Various methods have previously been used to find and assess severity of tender or trigger points. Among those commonly used are the pressure pain algometer with pressure pain threshold (PPT), range of motion electromyography and visual analog scales (VAS) (Aboodarda et al., 2015; Buttagat et al., 2012; Draper, 2015; Ghanbari et al., 2012; Kelencz et al., 2011; Nagrale et al., 2010; Simons & Travell, 1981; Sweety et al., 2014; Wong, 2012). Some studies have also utilized B-mode (two-dimensional) ultrasound imaging (US) to locate, define, trace, and quantify myofascial trigger points after palpation providing a useful means of quantification (Cojocaru MC, 2015; Kumbhare DA, 2016; Muller et al., 2014). Shear wave elastography ultrasound (SWE) has been used to calculate the elastic modulus (tissue stiffness) of muscle reliably, (Brandenburg et al., 2014; Eby et al., 2013; Gennisson et al., 2010; Kumbhare DA, 2016; Muller et al., 2014), but has not been used to quantify changes within trigger points following treatment.

Objectives

The purpose of our study was to quantify the effectiveness of PRT or TM at reducing pain, trigger point tenderness, and muscle stiffness in the upper trapezius muscle by using a combination of the visual analog scale, PPT, B-mode US and SWE to assess changes within trigger points.

METHODS

Participants

We recruited 60 healthy Participants, 24 males and 36 females, (age=27.1±8.8 years, wt=75.2±17.9 kg, ht= 172.8±9.7 cm) to participate in the study. Many of the participants participated on a University dance team. Participants admitted into the study were required to

have upper trapezius pain, during palpation, of at least 10 mm on the 100mm visual analog scale and muscle tightness with an accompanying trigger point in their upper trapezius. Participants who had suffered an acute injury to their upper trapezius in the last 6 days, were undergoing current treatment for their upper trapezius, or were unable to lie on their stomach for an extended amount of time were removed from the study.

The study was approved by the university's Institutional Review Board (IRB#17411) before participant recruitment. All participants provided written informed consent before individual data collection began.

Instruments

We used a GE LOGIC S8 ultrasound machine (4MDMedical, Lakewood, NJ) with the 9L soundhead to measure muscle thickness and stiffness. Muscle thickness was measured using B-mode ultrasound and SWE measured stiffness of the tissue.

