In order to quantify subjective perception of pain we used PPT algometer (Jtech Medical Commander Echo pressure algometer, Jtech Medical, Midvale, UT) with a $.5 \text{ cm}^2$ applicator tip along with the 100 mm visual analog scale.

Procedures

Figure 1 outlines study procedures. During the first visit participants underwent screening for presence of inclusion and exclusion criteria as well as palpation for trigger points, following guidelines by Simons, Travell and Speicher (Simons & Travell, 1981; Speicher, 2016). Each side was examined and pain produced during palpation was measured with previously published methods using the VAS (Crichton, 2001). The side that was to be treated was determined by the higher VAS score. Trigger point location, found through palpation, was marked so that all measurements were taken in the same location. All baseline measurements were taken

according to the methods listed below. The participants were then randomly assigned into one of two treatment groups, one being positional release therapy, the other therapeutic massage.

The same order of measurement was used for all participants since we felt that pressure from the PPT algometer could act as a treatment and influence the visual analog scale or elastography measures. Measurements were taken at rest with the participant in prone position, with their arms at their sides for all measurement series, before and after treatment.

[figure not shown]
Pain Pressure Threshold

Pain pressure threshold was determined by a digital pressure algometer on the same point identified during screening. The area was measured once by pressing perpendicularly into the trigger point until the subject declared it to be painful. The peak force measured was then recorded in kg.

Ultrasound and Elastography

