Participants in the PRT group received three successive treatments or releases in the marked area. The researcher located the marked trigger point and while maintaining contact, a light pressure with the clinician's fingertip was applied creating slight dimpling of the skin and blanching of the clinician's fingernail bed. Following palpation, the researcher moved the participant's shoulder into passive abduction and scapular upward rotation and retraction until a position of comfort was achieved with no pain reported by the participant, as directed by Speicher, "Clinical Guide to Positional Release Therapy" (Speicher, 2016) (Figure 3). The participant was instructed to remain completely relaxed during the 90 second treatment. After the recommended 90 seconds had passed the limb was returned to the starting position. This was repeated immediately 2 more times in tender points immediately adjacent to the first one, as recommended by Speicher (Speicher, 2016). Following treatment, the same dependent variable measurements were taken.

Posttreatment measurements

Each participant returned 48 hours post treatment, where dependent measurements were taken. Participants were also given an activity survey to record the number of hours they exercised between the last session and the current session to note any abnormalities or increase in normal exercise. The mark made from the first session, over the examined trigger point, was still visible at the second visit for all participants and was used to determine the location for performing dependent measurements.

Statistical Analysis

A mixed-models analysis of variance was performed for each of the dependent variables (VAS, US, elastography, and PPT). The covariates considered in the analysis were the participants' sex, side of treatment, height, weight, and age. A step-wise regression was used to determine significant covariates for each of the dependent variables. Following the step-wise regression the primary variables of interest, treatment and time of measurement were added along with their interaction for each of the dependent variables. Post hoc t-tests were used to evaluate differences in the measurements. All analyses were performed using SAS, version 9.4 (Chapel Hill, North Carolina) and alpha was set at $p < 0.05$.

References

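### Stepwise covariate selection without treatment or time in the model slightly shrinks the treatment main effect and makes covariate p-values unreliable, though the treatment-by-time test is untouched

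*Combined protocol and SAP*

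**What the plan says.** All of this is in the Statistical Analysis section unless noted.

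- Model: "A mixed-models analysis of variance was performed for each of the dependent variables (VAS, US, elastography, and PPT").
- Candidate covariates: "sex, side of treatment, height, weight, and age". All five are fixed within a participant.
- Selection: "A step-wise regression was used to determine significant covariates for each of the dependent variables".
- Order: "Following the step-wise regression the primary variables of interest, treatment and time of measurement were added along with their interaction", so selection is run with neither treatment nor time in the model.
- Post hoc t-tests follow, at the 0.05 level. The contrasts are not named.
- Participants section: "We recruited 60 healthy Participants, 24 males and 36 females".
- Procedures section: "The participants were then randomly assigned into one of two treatment groups". Baseline readings precede this step.
- Readings are taken before treatment, after treatment and at 48 hours. The Posttreatment measurements section says that each participant returned and that the skin mark "was still visible at the second visit for all participants".

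The plan gives no entry or stay threshold and does not say whether selection allowed for repeated readings. It names neither a fixed covariate set nor an unadjusted analysis.

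**The concern.** Two faults follow from the stated order.

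First, randomisation leaves some chance imbalance in every covariate. When treatment is absent from the selection model, any real treatment effect sits in the outcome unexplained. A covariate whose imbalance happens to line up with that effect is then more likely to be selected. Once in the final model it takes part of the effect with it, so the arm estimate is biased toward zero. At stake are the treatment main effect, since treatment is named among the variables of primary interest, and any post hoc comparison of the arms at a single time.

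Second, a covariate kept because its p-value was small cannot have that p-value read at face value. The problem is worse if each participant's three readings entered the selection as independent rows, because the candidates do not vary within a person.

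**Working it through.** The documents give no power, effect-size or SD figure on this point, so there is nothing of the plan's own to reproduce.

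**Inputs.** From the documents: 60 participants, two arms, three readings each, four outcomes, five participant-level candidates, alpha 0.05. Assumed: 30 per arm, two-sided tests, entry and stay at 0.05 or 0.15, within-person correlation r from 0.5 to 0.85, unit SD, covariates entered as main effects only.

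**1. Chance selection, one row per person.** For five independent noise covariates:

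- entry 0.05: 1 − 0.95^5 = 22.6% per outcome
- entry 0.15: 1 − 0.85^5 = 55.6% per outcome

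Stepwise simulations on participant means gave 19–23% and 51–55%.

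**2. Chance selection if the three readings were stacked.** For a covariate constant within a person, the naive variance is too small by the factor 1 + 2r. The true level of a nominal 5% test is 2 × (1 − Φ(1.96/√(1 + 2r))).

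| r | 1 + 2r | true level |
|---|---|---|
| 0.5 | 2.0 | 16.6% |
| 0.7 | 2.4 | 20.6% |
| 0.85 | 2.7 | 23.3% |

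In simulation, at least one of the five noise covariates was selected in about 55–69% of trials at entry 0.05 and 81–90% at entry 0.15.

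**3. Shrinkage of the treatment main effect.** If the arms differ by δ at both post-treatment readings and by nothing at baseline, the main effect averages to 2δ/3. With r = 0.7 and noise covariates on stacked rows at entry 0.05:

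- δ = 0.5: true 0.333, bias −0.0114, or −3.4%
- δ = 1.0: true 0.667, bias −0.0211, or −3.2%

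A separate set of 6,000 runs per setting used a participant variance of 0.6 and a residual variance of 0.4. Estimates as a ratio to the true value, over participant means or stacked rows and entry 0.05 or 0.15:

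| Covariates | δ | all five fixed | stepwise |
|---|---|---|---|
| noise | 0.6 | 1.003 | 0.964–0.984 |
| noise | 1.0 | 1.001 | 0.965–0.983 |
| prognostic | 0.6 | 0.991 | 0.943–0.959 |
| prognostic | 1.0 | 1.002 | 0.956–0.969 |

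The Monte Carlo error of these ratios is about 0.004–0.008. The arm contrast at 48 hours lost about 1–3%.

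**4. Size against sampling error.** The standard error of the main effect is about √((1 + 2r)/3) × √(2/30).

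- r = 0.7: 0.894 × 0.258 = 0.231. The biases are 0.0114/0.231 = 0.05 and 0.0211/0.231 = 0.09 of a standard error.
- r = 0.6: 0.856 × 0.258 = 0.221. The largest prognostic bias is (1 − 0.956) × 0.667 = 0.029, or 0.029/0.221 = 0.13 of a standard error.

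**5. False positives for treatment.** With no true effect, rejection rates under stepwise selection were 4.1–5.4% (main effect), 4.7–5.9% (interaction) and 4.4–6.0% (48-hour contrast), with Monte Carlo error of about 0.4 points.

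**6. Treatment-by-time interaction.** A covariate fixed within a person and entered as a main effect cancels from that person's change. In a mixed model fitted to complete simulated data with no covariates, two, or all five, the interaction coefficients were 0.636 and 0.644 each time, with standard error 0.256 each time. Only the treatment coefficient moved (0.068, −0.094, −0.074).

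**The case against.** The strongest reply is that no treatment conclusion is shown to change. The objective is change within trigger points, so the PRT–TM question sits in the treatment-by-time interaction, which selection cannot touch here. The main effect averages in a baseline reading taken before randomisation and is a weak measure of efficacy anyway. Main-effect power differs from that of the fixed model by about 2 points or less, in either direction. All of this stands, and it limits the point to a small one.

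Several stronger readings are tempting and are not supported:

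- **Selection produces false treatment effects.** It does not: type I error stays near 5%. The false significance concerns covariates, and the plan does not list covariate effects as an objective.
- **The PRT–TM difference in change is pulled toward zero.** It is not, in complete data.
- **The readings were stacked.** The plan does not say so. Selection could have used participant means or steps within the mixed model, so the 55–69% is conditional on stacking.
- **Different covariate sets make the four outcomes' arm differences incomparable.** In a randomised linear model each set targets the same arm difference for its outcome, and the plan makes no comparison across outcomes.

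It is also fair to say that naming covariates now is not true prespecification, because the document describes participants and analysis in the past tense. The remedy has to allow for that. What survives the reply is that the stated rule carries an avoidable bias and an unreliable by-product, and does nothing for the interaction.

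**Conclusion.** The concern holds in limited form. Outcome-driven selection without treatment in the model biases the treatment main effect toward zero by about 2–4% with noise covariates and by up to about 6% with prognostic ones. Single-time arm contrasts are affected in the same direction and somewhat less. The bias is roughly a tenth of a standard error, so it is unlikely to alter a conclusion. Covariates reported as significant would not be trustworthy, even in the best case of one row per person. Inference on change over time is intact.

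The sizes rest on a 30:30 split, the assumed correlations, covariate strengths and entry thresholds, and complete data. The documents support full return at 48 hours. With missing readings or another covariance structure, the interaction result would be approximate rather than exact. This is a change that should be made, not one on which the trial's validity depends.

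**What to change.** - Delete the stepwise step.
- Choose a fixed set from the five listed covariates, or take all five, on subject-matter grounds and without reference to the outcome data. Fit it in the same model as treatment, time and their interaction, whatever the p-values.
- Report an unadjusted analysis beside it. The data are already collected, and this shows directly whether the choice of covariates mattered.
- Do not present selected covariates as findings.

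The cost is a sentence of text, a rerun of four models and a few degrees of freedom out of about 58. If the covariates have no value, the arm standard error was about 1–2% larger with two fixed covariates in simulation. As a check, the expected inflation for k worthless normal covariates is √(1 + k/(60 − k − 3)). That is √(1 + 2/55) = 1.018 for two and √(1 + 5/52) = 1.047 for all five, so a short list is cheaper. If the covariates are prognostic, adjustment gains precision instead. The interaction's standard error is unchanged either way.

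### With baseline as a level of time, the PRT v TM contrast is a change score; adjusting for the baseline outcome would usually give a narrower interval from data already held

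*Combined protocol and SAP*

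**What the plan says.** Under Procedures, the outcomes are first recorded before allocation: "All baseline measurements were taken", and only afterwards, "The participants were then randomly assigned into one of two treatment groups". The same outcomes are recorded again directly after treatment and at a visit 48 hours later. The positioning instruction in that section applies "for all measurement series, before and after treatment", which treats the pre-treatment set as one of the measurement series.

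The Statistical Analysis section gives the covariates: "The covariates considered in the analysis were the participants' sex, side of treatment, height, weight, and age". Step-wise regression selects among these, and then "the primary variables of interest, treatment and time of measurement were added along with their interaction for each of the dependent variables". It adds: "Post hoc t-tests were used to evaluate differences in the measurements", without saying which differences. The baseline outcome is not on the covariate list, and nothing makes the two arms share a baseline mean.

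Two statements bear on the baseline VAS in particular. Entry required "upper trapezius pain, during palpation, of at least 10 mm on the 100mm visual analog scale", and "The side that was to be treated was determined by the higher VAS score".

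**The concern.** PRT v TM is the only randomised comparison, and it rests on 60 people. With baseline as a level of time, the interaction compares the arms on change from baseline. It spends information estimating a baseline difference whose true value is zero by design.

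A change score fixes the slope of the follow-up value on the baseline value at 1. A raw comparison of post-treatment values fixes it at 0. Estimating the slope gives, apart from a small degrees-of-freedom cost, a variance no larger than either. The listed covariates cannot take its place: they do not vary over time, so as main effects with complete data they cancel out of a change contrast.

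At stake is the width of the interval for PRT v TM. A wider interval than the data require makes it easier to misread an inconclusive result as showing that the two therapies are equivalent. The within-arm changes, which the stated purpose also covers, are not in question.

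**Working it through.** **Inputs.** From the documents: 60 participants, two randomised arms, three measurement times, alpha 0.05. Not in the documents, so assumed: 30 per arm, two-sided testing, complete data, no other covariates, post-treatment SD of 1, and the same correlation ρ between any two times. The plan has no power or precision figure to reproduce.

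**Variances at one post-treatment time.** Let b = baseline SD / post-treatment SD.

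- Raw post-treatment comparison: 1
- Change from baseline: 1 + b² − 2ρb, which is 2(1−ρ) when b = 1
- Baseline-adjusted: 1 − ρ²

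Change minus adjusted is (b − ρ)², which is never negative. With b = 1, adjusted/change is (1+ρ)/2, that is 0.65, 0.75 and 0.85 at ρ = 0.3, 0.5 and 0.7. To match the adjusted analysis at 30 per arm, a change analysis would need 30 / ((1+ρ)/2), about 46, 40 and 35 per arm.

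**95% CI half-width, equal SDs.** Half-width = t × √(2 × variance / 30), with 58 df for raw and change and 57 df for adjusted. The adjusted variance is also multiplied by 1 + 1/56 for chance baseline imbalance. At ρ = 0.5:

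- Change: 2.002 × √(2 × 1 / 30) = 0.517
- Adjusted: 2.002 × √(2 × 0.75 × 1.0179 / 30) = 0.452

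| ρ | Raw | Change | Adjusted | Adjusted/change | Adjusted/change, change on 116 df |
|---|---|---|---|---|---|
| 0.3 | 0.517 | 0.612 | 0.498 | 0.814 | 0.822 |
| 0.5 | 0.517 | 0.517 | 0.452 | 0.874 | 0.883 |
| 0.7 | 0.517 | 0.400 | 0.373 | 0.930 | 0.940 |
| 0.8 | 0.517 | 0.327 | 0.313 | 0.957 | 0.968 |
| 0.9 | 0.517 | 0.231 | 0.227 | 0.984 | 0.994 |
| 0.95 | 0.517 | 0.163 | 0.163 | 0.997 | 1.007 |

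The last column takes the change contrast from a three-time compound-symmetry model. Break-even is near ρ = 0.96 against the simple change analysis and about 0.92–0.93 against the compound-symmetry model.

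**How often a single trial gains.** In 5,000 simulated trials per setting, the adjusted interval was narrower than the change interval in 99% of trials at ρ = 0.5, 94% at 0.7, 85% at 0.8, 64% at 0.9 and 46% at 0.95. Against the compound-symmetry model the figures were 96%, 79%, 68%, 54% and 47%.

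**Power, assumed true difference 0.6 SD, ρ = 0.3 / 0.5 / 0.7** (noncentral t or F, without the imbalance factor):

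- One time: change 49 / 63 / 84%; raw 63% throughout; adjusted 67 / 75 / 89% (66 / 74 / 89% by simulation).
- Two-df test, difference present at both post-treatment times: interaction 50 / 66 / 87%; adjusted joint test 78 / 82 / 93%.
- Two-df test, difference at one time only: the interaction is unchanged; adjusted joint test 58 / 70 / 89%.

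**Unequal SDs, one time.** Adjusted power does not depend on b.

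- b = 1.33: change power 37 / 48 / 67%, so adjustment gains more.
- b = 0.75: change power 58 / 72 / 89%, so the gain is 9 / 3 / 0 points. With a difference at one time only, the joint test does not reliably beat the interaction (simulated 57 / 69 / 88% v 56 / 71 / 90%).

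Equal SDs are doubtful for VAS, because its baseline was selected by the entry threshold and by treating the more painful side.

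**Type I error.** In simulation the adjusted tests rejected a true null in 4.7–5.3% of trials, across equal SDs, b = 1.33, b = 0.75 and a baseline truncated at its median.

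**The case against.** The strongest reply is that the plan contains no error. A treatment, time and interaction model is a standard repeated-measures analysis, and its contrast is unbiased. That is right, and it limits the point to efficiency.

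The levels of time are never defined. The phrase about measurement before and after treatment comes from a sentence on body position, and the post hoc t-tests are unspecified. This stands as a condition on the claim. It does not rescue the plan's precision, though: if those tests compare raw values at one time, adjustment still gives a narrower interval once ρ exceeds about 0.2.

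The benefit rests wholly on assumed correlations and SDs, and it fades when measurements are highly repeatable. This also stands. Measurements were taken at one marked spot, with thickness averaged over two images and stiffness over nine sample circles, so a high ρ cannot be ruled out for these outcomes. The largest power gain, 27 points (unrounded values), needs ρ = 0.3 and a difference sustained at both times.

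Finally, the stated purpose can be read as asking whether either therapy works, with no superiority hypothesis, and any reanalysis now is post hoc. Both are fair reasons for modest weight. They are not reasons to report the randomised comparison less precisely than the data allow.

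**Conclusion.** The point holds as something the sponsor should consider: a valid analysis that usually leaves precision unused. Provided baseline is a level of time, the PRT v TM interaction contrast is a change score. In large samples, adjusting for baseline at a single post-treatment time cannot do worse than that or than a raw comparison. At 60 participants the exceptions are small: very high ρ against a change analysis, and ρ below about 0.2 against a raw one. For the two-df test the advantage is not assured in every setting.

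The direction is well supported; the size cannot be fixed from the documents. Under the stated assumptions the interval narrows by about 19%, 13% and 7% at ρ = 0.3, 0.5 and 0.7, by 4% at 0.8 and 2% at 0.9, and by nothing material at 0.95.

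**What to change.** For PRT v TM, model the immediate and 48-hour values of each outcome with time, treatment by time and baseline by time, an unstructured within-participant covariance and Kenward-Roger degrees of freedom. With complete data this is baseline-adjusted ANCOVA at each time. Force the baseline outcome in, so that step-wise selection cannot drop it, and keep the other covariates as in the original model. Report the adjusted difference and 95% CI immediately after treatment and at 48 hours, with the joint two-df test as the single overall test per outcome. Do not use a treatment main effect that averages in the baseline time. The SAP should also state the levels of time and which contrasts the t-tests make.

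An alternative, equivalent in large samples, keeps all three times and constrains the arms to a common baseline mean. It needs small-sample standard errors: without them a true null was rejected in 5.6–5.9% of simulated trials for the joint test. Within-arm changes can come from that model or from the original one.

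The cost is SAS code, a short SAP edit and one degree of freedom per post-treatment time. If ρ were 0, the adjusted half-width would be 0.522 SD against 0.517 SD for the raw comparison. No new data are needed. Because the document describes completed work, label this a post hoc revised analysis and show it beside the original model. It does not settle multiplicity across the four outcomes.

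### With baseline apparently a level of time, the treatment main effect dilutes the PRT-TM difference, and the plan does not say which contrast is the between-group test

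*Combined protocol and SAP*

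**What the plan says.** In Procedures, "All baseline measurements were taken" first, and "The participants were then randomly assigned into one of two treatment groups". Readings were made at rest "for all measurement series, before and after treatment". Under the treatment descriptions, "Following treatment, the same dependent variable measurements were taken" (the massage paragraph says the same in other words). Under Posttreatment measurements, "Each participant returned 48 hours post treatment, where dependent measurements were taken". Each outcome therefore has three readings, the first taken before allocation.

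Statistical Analysis describes a mixed-model analysis of variance for each of four outcomes (VAS, ultrasound thickness, elastography, PPT). The candidate covariates, screened by stepwise regression, are sex, side, height, weight and age. Then "the primary variables of interest, treatment and time of measurement were added along with their interaction", followed by post hoc t-tests that are not specified further, at alpha 0.05. The baseline value of the outcome is not among the covariates. Under Objectives, "The purpose of our study was to quantify the effectiveness of PRT or TM". No section says which term or contrast compares PRT with TM.

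**The concern.** If baseline is a level of time, the treatment term is the arm difference averaged over three readings, one of which treatment cannot have affected. Randomisation makes the true difference at that reading zero, so the term understates the PRT-TM difference by a fixed proportion. It also picks up part of any chance imbalance at baseline. The plan calls treatment a primary variable of interest, and nothing in it sets this term aside.

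Two things are at stake. The objective is to quantify effectiveness, and an estimate read from this term would be too small. In addition, a non-significant treatment term could be reported as no difference between the therapies when other contrasts in the same data show one.

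**Working it through.** **Inputs from the documents.** 60 participants (Participants section), two randomised arms, three readings per outcome, alpha 0.05.

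**Assumptions.** 30 per arm (arm sizes are not given), two-sided testing, equal SD at each reading (set to 1), the same correlation r between any two readings, equal weighting of the three times, and baseline as a level of time. The documents give no SD, correlation, effect size or power, so there is no planned figure to reproduce, and r and the effect D are varied.

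**Step 1: what the main effect estimates.** With true arm differences 0, D1 and D2 at the three readings, it estimates (0 + D1 + D2)/3.
- Equal at both later readings: (0 + D + D)/3 = 0.67D. A 20,000-run simulation gave ratios of 0.671 and 0.667.
- Halved by 48 hours: (0 + D + D/2)/3 = 0.50D.
- Immediate only: (0 + D + 0)/3 = 0.33D.

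This step needs no SD or correlation.

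**Step 2: baseline imbalance.** The regression of a person's three-reading mean on the baseline reading has slope (1 + 2r)/3. An observed baseline imbalance therefore enters the term with expected weight 0.53, 0.67, 0.80 and 0.90 at r = 0.3, 0.5, 0.7 and 0.85.

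**Step 3: power for a sustained effect.** The standard errors are:
- main effect: sqrt[(2/30)(1 + 2r)/3], for an effect of 2D/3;
- mean of the two later readings minus baseline: sqrt[(2/30)(1.5)(1 − r)], for an effect of D;
- baseline-adjusted mean of the two later readings: sqrt[(2/30)((1 + r)/2 − r²)], for an effect of D.

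The interaction is an F test on 2 and 116 df. Its noncentrality is the sum of squared deviations of (0, D, D) from their mean, divided by (2/30)(1 − r).

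With D = 0.5 and r = 0.5:
- main effect: 0.333/0.211 = 1.58, 58 df, power 34%;
- interaction: 0.1667/0.0333 = 5.0, power 49%;
- mean change: 0.5/0.224 = 2.24, 58 df, power 59%;
- baseline-adjusted mean: 0.5/0.183 = 2.74, 57 df, power 77%.

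| Power, D = 0.5 sustained | r = 0.3 | r = 0.5 | r = 0.7 | r = 0.85 |
|---|---|---|---|---|
| Treatment main effect | 41% | 34% | 30% | 27% |
| Treatment-by-time interaction | 37% | 49% | 72% | 96% |
| Mean change from baseline | 46% | 59% | 81% | 98% |
| Baseline-adjusted post mean | 72% | 77% | 89% | 99% |

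Unequal arms change little. Main-effect power at D = 0.5, r = 0.5 is 34% for 30/30, 34% for 25/35 and 31% for 20/40.

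**Step 4: immediate-only effect, D = 0.5, r = 0.5.** The main effect estimates 0.17 SD with 12% power, and the interaction has 49%. The baseline-adjusted post mean is itself halved here and has 27%. The baseline-adjusted immediate difference has SE sqrt[(2/30)(1 − r²)] = 0.224, ratio 2.24 on 57 df, and 59%. The two times are therefore needed separately as well as averaged.

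**Step 5: larger effects.** Main-effect power passes 50% at about 0.55 SD (r = 0.3) to 0.71 SD (r = 0.8). For a sustained 0.8 SD effect it is 79%, 70%, 62% and 59% at r = 0.3, 0.5, 0.7 and 0.8.

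**The case against.** The strongest reply is that the quoted sentence names variables, not a test. It may only separate the design variables from the screened covariates. The same sentence adds the interaction, which tests whether change from baseline differs between arms, and t-tests follow. For a sustained 0.5 SD effect the interaction has 49% to 96% power at r from 0.5 to 0.85, so comparing a remedy only with the main effect flatters the remedy. This stands. A reader might infer that the plan makes the main effect its primary test, or that the planned analysis would miss a real difference. The documents support neither.

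A reader might also infer that the main effect usually misses a true difference. That holds only for small to moderate effects and fails at 0.8 SD for every correlation tried. Nor does the term carry baseline imbalance in full: the expected weight is (1 + 2r)/3.

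Unadjusted change is not always better either. At r of about 0.25 it ties with the main effect (43.5% each at D = 0.5), and at r = 0.2 it is weaker (41% against 46%). PPT is a single press, so a low correlation cannot be excluded. This counts in favour of baseline adjustment over simple change.

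Finally, baseline as a level of time is inferred. If only the two later readings were levels, the dilution would vanish. But the model description gives baseline no other place, so the inference is the natural one.

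What the reply leaves untouched is that the plan does not say that the interaction, or any particular t-test, answers PRT versus TM. A 2-df F test also gives neither a size nor a direction.

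**Conclusion.** The concern holds in a limited form. On the natural reading of the model, the treatment main effect is not the PRT-TM treatment effect. It is two thirds of a difference equal at both later readings, half of the immediate difference if that halves by 48 hours, and one third if it is gone by then. Two thirds is thus not a general factor. The dilution is arithmetic, given baseline as a level of time and equal weighting. The power figures also rest on 30 per arm, two-sided 0.05, equal SDs and equal correlations, none of which the documents state.

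The defect is one of specification. A model that could answer the between-group question is fitted, but the term or contrast that answers it is not named, while a term that should not be used for it is given prominence.

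**What to change.** State that the treatment main effect is neither tested nor interpreted as the PRT-TM comparison while baseline is a level of time. Take the comparison from a baseline-adjusted analysis of the two post-treatment readings. Either enter the baseline value as a covariate, fixed in the model and not subject to stepwise selection, or keep all three readings and constrain the arms to be equal at baseline. Use the mean of the two later readings as the single summary. Report the immediate and 48-hour differences separately, each with a 95% confidence interval.

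The cost is SAP wording, a small change to the model and three contrasts per outcome. No new data are needed. The downside is that three contrasts on four outcomes make 3 × 4 = 12 comparisons, so one should be named as the main one for each outcome. The section is written in the past tense. If results have already been seen, the report should say that the contrast was chosen afterwards.
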